15.0 STUDY TERMINATION

The study will terminate as described in section 15.0. The Principal Investigator, the IRB, and the FDA reserve the right to terminate this study at any time.

APPENDIX A: TREATMENT-RELATED MORTALITY (TRM) SCORE

Calculation of Simplified Treatment-Related Mortality (TRM) Score

Includes covariates: performance status (PS), age, platelet count, albumin, secondary AML, white blood cell count (WBC), peripheral blood blast percentage, and creatinine

Score = $100/(1+e^{(-x)})$, with $x = -4.08 + 0.89*PS + 0.03*age - 0.008*platelet count - 0.48*albumin + 0.47*(have secondary AML) + 0.007*WBC - 0.007*(peripheral blood blast percentage) + 0.34*creatinine$

Probability of TRM Above and Below Various Simplified TRM Score Cut-offs

TRM Score Interval	Patients below/within/above TRM Score Interval (%)	TRM Probability if below TRM Score Interval (%)	TRM Probability if within TRM Score Interval (%)	TRM Probability if above TRM Score Interval (%)
0 – 1.9	0/20/80	-	1	12
1.91 – 3.9	20/20/60	1	2	16
3.91 – 6.9	40/20/40	1	7	20
6.91 – 9.2	60/10/30	3	7	24
9.21 – 13.1	70/10/20	4	12	31
13.11 – 22.8	80/10/10	5	20	41
22.81 – 100	90/10/0	6	41	-

From: Walter RB, Othus M, Borthakur G, Ravandi F, Cortes JE, Pierce SA, Appelbaum FR, Kantarjian HM, Estey EH. Prediction of early death after induction therapy for newly diagnosed acute myeloid leukemia with pretreatment risk scores: a novel paradigm for treatment assignment. *J Clin Oncol*. 2011;29(33):4417-4424.

APPENDIX B: CARDIOTOXICITY INDEX OF ANTHRACYCLINES

Drug	Schedule	Relative Myelosuppressive Potency ¹	Approximate Relative Cardiotoxicity	Cardiotoxicity Index ²
Doxorubicin	Rapid infusion	1	1	1
Doxorubicin	24hr infusion	1	0.62	0.62
Epirubicin	Rapid infusion	0.67	0.66	0.44
Mitoxantrone	Rapid infusion	5	0.5	2.5
Daunorubicin	Rapid infusion	0.67	0.75	0.5
Idarubicin	Rapid infusion	5	0.53	2.67

¹Of single dose compared with doxorubicin administered by standard schedule. ²The cardiotoxicity index represents a factor by which to multiply the cumulative dose of a drug administered to obtain an approximation of toxicity that might be expected had the resultant amount of doxorubicin been given by rapid infusion

Adapted from Holland J, et al. Cancer medicine, 5th ed. American Cancer Society. Hamilton and London: B.C. Decker, Inc. 2000.

APPENDIX C: EUROPEAN ORGANIZATION FOR RESEARCH AND TREATMENT OF CANCER QLQ-C30 QUESTIONNAIRE

EORTC QLQ-C30 (version 3)

We are interested in some things about you and your health. Please answer all of the questions yourself by circling the number that best applies to you. There are no "right" or "wrong" answers. The information that you provide will remain strictly confidential.

Please fill in your initials:

Your birthdate (Day, Month, Year):

Today's date (Day, Month, Year):

31

1. Do you have any trouble doing strenuous activities, like carrying a heavy shopping bag or a suitcase?
2. Do you have any trouble taking a long walk?
3. Do you have any trouble taking a short walk outside of the house?
4. Do you need to stay in bed or a chair during the day?
5. Do you need help with eating, dressing, washing yourself or using the toilet?

Not at All	A Little	Quite a Bit	Very Much
------------	----------	-------------	-----------

1	2	3	4
1	2	3	4
1	2	3	4
1	2	3	4
1	2	3	4

During the past week:

6. Were you limited in doing either your work or other daily activities?
7. Were you limited in pursuing your hobbies or other leisure time activities?
8. Were you short of breath?
9. Have you had pain?
10. Did you need to rest?
11. Have you had trouble sleeping?
12. Have you felt weak?
13. Have you lacked appetite?
14. Have you felt nauseated?
15. Have you vomited?
16. Have you been constipated?

Not at All	A Little	Quite a Bit	Very Much
------------	----------	-------------	-----------

1	2	3	4
1	2	3	4
1	2	3	4
1	2	3	4
1	2	3	4
1	2	3	4
1	2	3	4
1	2	3	4
1	2	3	4
1	2	3	4
1	2	3	4

Please go on to the next page

During the past week:	Not at All	A Little	Quite a Bit	Very Much
17. Have you had diarrhea?	1	2	3	4
18. Were you tired?	1	2	3	4
19. Did pain interfere with your daily activities?	1	2	3	4
20. Have you had difficulty in concentrating on things, like reading a newspaper or watching television?	1	2	3	4
21. Did you feel tense?	1	2	3	4
22. Did you worry?	1	2	3	4
23. Did you feel irritable?	1	2	3	4
24. Did you feel depressed?	1	2	3	4
25. Have you had difficulty remembering things?	1	2	3	4
26. Has your physical condition or medical treatment interfered with your family life?	1	2	3	4
27. Has your physical condition or medical treatment interfered with your social activities?	1	2	3	4
28. Has your physical condition or medical treatment caused you financial difficulties?	1	2	3	4

For the following questions please circle the number between 1 and 7 that best applies to you.

29. How would you rate your overall health during the past week?

1 2 3 4 5 6 7

30. How would you rate your overall quality of life during the past week?

1 2 3 4 5 6 7

APPENDIX D: MANAGEMENT OF TOXICITIES SPECIFIC TO SORAFENIB

I. Prevention/management strategies for diarrhea and fatigue

Diarrhea and fatigue are common side effects of sorafenib. The same dose-modification algorithm used for skin toxicities can be used to address these toxicities. However, the preventive/management strategies for diarrhea and fatigue should be consistent with local standards (e.g., anti-diarrheals and optimized hydration status for diarrhea).

II. Hand-foot-skin reaction: Suggested sorafenib dermatologic toxicity modification

Recommended dose modification for hand foot skin reaction (HFSR)		
Toxicity Grade		Suggested dose modification
Grade 1	Any occurrence	Maintain dose level and consider topical therapy for symptomatic relief
Grade 2	1 st occurrence	Maintain dose level and consider topical therapy for symptomatic relief If no improvement within 7 days, see below
	No improvement within 7 days or 2 nd occurrence	Interrupt until resolved to Grade 0-1 When resuming treatment, decrease dose by one dose level
	3 rd occurrence	Interrupt until resolved to Grade 0-1 When resuming treatment, decrease dose by two dose levels
	4 th occurrence	Discontinue treatment permanently
Grade 3	1 st occurrence	Interrupt until resolved to Grade 0-1 When resuming treatment, decrease dose by one dose level
	2 nd occurrence	Interrupt until resolved to Grade 0-1 When resuming treatment, decrease dose by two dose levels
	3 rd occurrence	Discontinue treatment permanently

At first occurrence of HFSR, independent of grade, prompt institution of supportive measures such as topical emollients, low potency steroids, or urea-containing creams should be administered.

Recommended prevention/management strategies for skin toxicities consistent with HFSR are summarized below.

Recommended Prevention/Management Strategies for Skin Toxicities Consistent with Hand-Foot-Skin-Reaction	
Toxicity Grade	Practical Prevention / Management Strategies for HFSR
Grade 0 (Preventive strategies)	
 • Maintain frequent contact with trial physician to ensure early diagnosis of HFSR. • Practical prevention strategies 
 ◦ Pedicure^a for subjects with pre-existing hyperkeratosis. ◦ Subjects should avoid hot water, and clothing or activities that can cause friction on the skin. ◦ Moisturizing cream should be applied sparingly. • Padded gloves and open shoes with padded soles should be worn to relieve pressure points.
Grade 1 Any occurrence	
 • Continue preventive strategies and in addition: 
 ◦ Soak hands in cool water. ◦ Apply petroleum jelly to moist skin. • In the case of hyperkeratotic lesions, exfoliate the hands or feet and apply moisturizing cream immediately afterwards.
Grade 2 Any occurrence or Grade 3 Any occurrence	
 • Continue supportive/management measures and add analgesic(s) for pain.
a: Pedicure should be done by a podiatrist.	

III. Treatment-emergent hypertension

Hypertension is a known and potentially serious AE associated with sorafenib treatment. Subjects will undergo brief physical examinations, including blood pressure monitoring, on a weekly basis through the first 6 weeks of therapy. Thereafter, blood pressure will be monitored on Day 1 of each cycle.

Blood pressure measurements considered out of the normal range are diastolic pressure > 90 mm Hg and/or systolic pressure > 140 mm Hg, or a 20 mm Hg increase in diastolic pressure if the previous measurement was within normal limits.

The dose-modification schedule to be followed in the event of treatment-emergent hypertension is outlined below. The choice of anti-hypertensive medication to be used in cases of treatment-emergent hypertension will be at the investigator's discretion and based on site-specific treatment guidelines as applicable. All anti-hypertensive medications used for the management of treatment-emergent hypertension should be recorded in the subject's records.

Once a dose-reduction modification has been made for treatment-emergent hypertension, NO dose re-escalation will be allowed.

Management of Treatment-Emergent Hypertension	
Grade of Event (NCI-CTCAE v4.0)	Management/ Next Dose
Grade 1	Consider increasing blood pressure monitoring. Continue sorafenib dosing as scheduled.
Grade 2 asymptomatic and diastolic pressure 90-99 mm Hg	Begin anti-hypertensive therapy. Continue sorafenib dosing as scheduled.
Grade 2 (symptomatic/persistent) OR Grade 2 symptomatic increase by > 20 mm Hg (diastolic) or to > 140/90 mm Hg if previously within normal limits OR Grade 3	Sorafenib should be held ^a until symptoms resolve and diastolic blood pressure < 90 mm Hg; also treat subject with anti-hypertensives and when sorafenib is restarted, reduce by 1 dose level. ^b If diastolic blood pressure is not controlled (< 90 mm Hg) on anti-hypertensive therapy, reduce another dose level. ^b
Grade 4	Discontinue sorafenib

a: Subjects requiring a delay of > 30 days (modify according to study specific cycle length) should discontinue sorafenib unless, in the opinion of the treating physician, the subject may benefit from continued treatment.

b: Subjects requiring dose reductions beyond 200 mg (1 placebo tablet) twice daily, every other day, should discontinue sorafenib.

Appendix E: Study Medication Diary

Principal Investigator:	[name]	Sponsor:	Bayer Pharmaceuticals
Protocol Number:	9510	Sponsor Study #:	CC9510
Title or Brief Description:	G-CLAM+Sorafenib in Newly Diagnosed AML/High-grade Myeloid Neoplasms		

Subject Name	Date of Birth	Study ID	
Study Medication	Sorafenib	Dose 400 mg (2 tablets) twice daily	Date Dispensed

Patient instructions:

- Check the box each time you take your pills every day on the diary below.
- Please bring all unused study medication, along with this drug diary, if you go to the hospital for any reason.
- Please return your sorafenib pill bottle (even if empty) and this drug diary to your doctor at your next appointment following your last dose of sorafenib.
- If you have any questions on your sorafenib dose or schedule, you can page us 24 hours a day through the UW paging operator at [contact]. From 8 am – 5 pm Monday-Friday ask to page [name] (research coordinator). For after hours and on the weekends, ask to page [name].

Patient Signature

Date

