- 6.3.1 For induction: patients will receive sorafenib and mitoxantrone at 1 of 6 total dose levels as allocated (see section Dose Escalation Scheme page 2 or 15.1.2). Mitoxantrone will be given IV daily over 60 minutes Days 1-3 and sorafenib orally Days 10-19 for all levels. Allowances of +/- 2 days for this window will be allowed for logistical purposes. Levels are as follows: Level 1, mitoxantrone 10 mg/m² with sorafenib 200 mg PO twice daily; Level 2, mitoxantrone 12 mg/m² with sorafenib 200 mg PO twice daily; Level 3, mitoxantrone 15 mg/m² with

sorafenib 200 mg PO twice daily; Level 4, mitoxantrone 18 mg/m² with sorafenib 200 mg PO twice daily; Level 5, mitoxantrone 18 mg/m² with sorafenib 400 mg PO in the morning and 200 mg in the evening; Level 6, mitoxantrone 18 mg/m² with sorafenib 400 mg PO twice daily. Level -1, dosed at mitoxantrone 10 mg/m² and sorafenib 200 mg PO once daily will also be available for dose de-escalation due to toxicities, as described in Section 6.8. For baseline organ dysfunction within the allowable limits of the eligibility criteria, dose reduction of individual medications specific to the organ impairment (e.g. liver, kidney) are allowed but not required, as described in section 6.10, and should be done in conjunction with the Oncology Pharmacist and PI.

- 6.3.2 The dose of mitoxantrone is calculated using the patient's actual weight.
- 6.3.3 For post-remission therapy: sorafenib will be given per dose level as above, starting on day 8 until day 27 or 3 days prior to next cycle of treatment, whichever occurs first. Allowances of +/- 3 days for this window will be allowed for logistical purposes (i.e. timing of clinic visit for count evaluation).
- 6.3.4 For maintenance: sorafenib will be given daily for up to 12 months following post-remission at the final dose the patient received during induction, with subsequent dose adjustment based on blood counts and extra-medullary toxicities.
- 6.3.5 All treatment is given as intent-to-treat; missed doses will not be made up.

6.4 **Administration of G-CSF, Cladribine, and Cytarabine**

- 6.4.1 The doses of the elements of G-CLAM chemotherapy will be as follows: G-CSF 5 µcg/kg rounded to 300 or 480 µcg daily subcutaneously daily on Days 0-5, Cladribine 5 mg/m² IV daily over 2 hours on Days 1-5, and Cytarabine 2 g/m² IV daily over 2 hours on Days 1-5.
- 6.4.2 The doses of G-CSF, cladribine, and cytarabine are calculated using the patient's actual weight.

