6.9 Maintenance Therapy

- 6.9.1** Patients in MRDneg CR at the end of post-remission therapy with G-CLA+sorafenib can continue to receive sorafenib for up to 12 months, as long as it is tolerated and as long as an MRDneg CR is maintained. Sorafenib will be given daily at the assigned dose level, unless dose reductions are needed for toxicity, in which case that dose would be continued. The MRDneg CR state should be confirmed every 3 months with bone marrow evaluations.

6.10 Dose Modifications of Chemotherapeutic Drugs for Baseline Organ Dysfunction or Subsequent Treatment Cycles

For patients with baseline organ dysfunction within the allowed limits of the eligibility criteria, or for those who experienced \geq Grade 3 non-hematologic toxicities excluding neutropenic fever and infections during the first induction, a dose reduction is

recommended. The following dose modifications are suggested for all subsequent treatment cycles:

6.10.1 If a patient develops Grade ≥ 3 non-hematologic toxicity other than Grade 3 infections within 28 days from the last dose of G-CLAM, the next course of G-CLAM will be given once toxicity is $<$ grade 2. The following dose reductions can be considered: cladribine 4 mg/m² days 1-5, cytarabine 1.5 g/m² days 1-4, mitoxantrone at one dose level below initial regimen days 1-3, G-CSF dose unchanged, and sorafenib at one dose level below their initial regimen. Additionally, the mitoxantrone may be omitted entirely if a 2nd induction course is indicated (any response less than CR without MRD) per treating physician discretion in discussion with the PI. Assuming these doses are well-tolerated the first course of G-CLA will be administered at these doses, omitting mitoxantrone. If Grade ≥ 3 non-hematologic toxicity occurs again, there will be a further reduction in doses of cladribine to 3 mg/m² daily days 1-5 and cytarabine to 1 g/m² daily days 1-5 for the first cycle of G-CLA. Doses for subsequent courses of G-CLA will be discussed with the Principal Investigator. Patients who were receiving dose level -1 sorafenib or mitoxantrone when grade ≥ 3 toxicity occurred will be taken off study.

6.10.2 Mitoxantrone: Reduce mitoxantrone dose by 50% if the bilirubin concentration is 1.5-4.5 x IULN and to 25% if the bilirubin concentration is > 4.5 x IULN. As per 6.10.1 can omit mitoxantrone entirely if clinically indicated.

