14.0 STATISTICAL CONSIDERATIONS

14.1 Phase 1

14.1.1 General Considerations: DLTs are defined in Section 8.3. DLTs occurring during Cycle 1 will be used to guide dose escalation. However, before the phase 2 portion is begun, all grade ≥ 3 adverse events of all patients treated in the phase 1 portion will be reviewed to assess for late and cumulative toxicities that were not captured during the phase 1 portion of the trial. The Principal Investigator reserves the right to modify the protocol to reduce the drug doses identified in the phase 1 portion if this assessment suggests a significant risk of late/cumulative toxicities. Patients will be considered evaluable for DLT if they received at least 75% of the assigned doses of each chemotherapeutic during Cycle 1 or if they developed a DLT. If a patient does not develop a DLT but does not receive at least 75% of treatment during Cycle 1, the patient will be considered not evaluable for DLT and will be replaced. Maximum tolerated dose (MTD) is defined as the highest dose studied in which the incidence of DLT is $<33\%$ assuming at least 6 patients have been treated at this dose.

14.1.2 Dose Escalation scheme:

Starting with dose level K=1:

A. Evaluate 6 patients at dose level K

- a. If 0 or 1 have DLT, increase dose to K+1 and go to A
- b. If 2 have DLT, stop dose escalation
- c. If >2 have a DLT, go to dose K-1

The dose level below that which dose escalation was stopped is the potential MTD.

In order to better define safety and initial evidence of anti-leukemia activity while waiting for patients to complete their treatment cycles to assess the MTD, any dose level cohort may be expanded up to 12 patients, provided that

2 or fewer of 6 patients had DLT at that dose level (ie at least 4/6 have had no DLT). the cohort is expanded to 7-11 patients, these patients will not count toward DLT and MTD evaluation. If a cohort is expanded to 12 patients, the following rules will determine further dose escalation:

If 3 or fewer have DLT, increase dose to K+1 (go to A)

If 4 or more have DLT, stop dose escalation

Dose-finding for both mitoxantrone and sorafenib:

Level 1	Mitoxantrone10 mg/m ²	Sorafenib 200 mg BID
Level 2	Mitoxantrone12 mg/m ²	Sorafenib 200 mg BID
Level 3	Mitoxantrone15 mg/m ²	Sorafenib 200 mg BID
Level 4	Mitoxantrone18 mg/m ²	Sorafenib 200 mg BID
Level 5	Mitoxantrone18 mg/m ²	Sorafenib 400mg AM, 200 mg PM
Level 6	Mitoxantrone18 mg/m ²	Sorafenib 400 mg BID

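### The only medication diary shows one sorafenib dose, which matches level 6 alone and conflicts with every other dose level and with any sorafenib reduction

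*Combined protocol and SAP*

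**What the plan says.** Appendix E, the study medication diary, gives the sorafenib dose as "Dose 400 mg (2 tablets) twice daily". It names no dose level, cycle or phase. The table of contents lists no other diary.

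Section 6.3.1 makes the sorafenib dose depend on the level: "patients will receive sorafenib and mitoxantrone at 1 of 6 total dose levels as allocated". Levels 1 to 4 carry "Sorafenib 200 mg BID" in the table in 14.1.2. Section 6.3.1 sets level 5 as "sorafenib 400 mg PO in the morning and 200 mg in the evening" and level 6 as "sorafenib 400 mg PO twice daily". For level -1 it says that "sorafenib 200 mg PO once daily will also be available for dose de-escalation due to toxicities". The dose tables at the front of the protocol agree with these.

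The dose can also change within a patient. After grade 3 or higher non-hematologic toxicity, 6.10.1 lets the investigator consider "sorafenib at one dose level below their initial regimen". Appendix D suggests reductions of one or two dose levels for hand-foot skin reaction, and of one level and then another for hypertension. Post-remission dosing follows the assigned level (6.3.3). Maintenance runs for up to 12 months at the last induction dose, subject to later adjustment (6.3.4, 6.9.1).

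**The concern.** The diary goes to the patient and puts a dose and a tablet count beside the name of the study drug. In a trial with four different sorafenib doses across seven levels, plus reductions for toxicity, one stated dose cannot be right for everyone who receives the form. Where it is wrong it is always too high.

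What is at stake is mainly clarity and safety for the patient. Someone assigned a lower dose, or just reduced because of toxicity, could hold a form showing a higher dose than the one prescribed. The form comes back at the visit after the last sorafenib dose, so it does not itself prompt an earlier check. If it were used unchanged through maintenance, the mismatch could last for months.

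**Working it through.** The plan gives no derived figure to reproduce. The check compares total daily doses.

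Inputs:
- Diary dose (Appendix E): 400 mg × 2 = 800 mg a day.
- Tablet strength: the diary equates 400 mg with 2 tablets, so 200 mg each. The hypertension footnote in Appendix D agrees: "Subjects requiring dose reductions beyond 200 mg (1 placebo tablet) twice daily, every other day, should discontinue sorafenib". It is used here only for tablet strength.
- Assigned dose by level: 6.3.1, 14.1.2 and the front tables.

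Ratio = diary daily dose ÷ assigned daily dose.

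| Level | Assigned mg a day | Tablets a day | Ratio |
|---|---|---|---|
| 1, 2, 3, 4 | 200 × 2 = 400 | 2 | 800/400 = 2.0 |
| 5 | 400 + 200 = 600 | 3 | 800/600 = 1.33 |
| 6 | 400 × 2 = 800 | 4 | 800/800 = 1.0 |
| -1 | 200 × 1 = 200 | 1 | 800/200 = 4.0 |

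The diary matches 1 of 7 levels and exceeds the assigned dose at the other 6.

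For a level 6 patient whose sorafenib is reduced, counting down the trial's own levels:
- One level lower is level 5, 600 mg a day: 800/600 = 1.33.
- Two levels lower is level 4, 400 mg a day: 800/400 = 2.0.

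A level 6 patient in whom only cladribine, cytarabine or mitoxantrone is reduced still matches the diary. The mismatch therefore concerns sorafenib reductions, not every dose reduction.

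**The case against.** Several points can fairly be made against this.

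- **The form may be meant for level 6.** The diary dose equals the top planned level, and phase 1 may end with completion of level 6 (14.2). The documents neither say nor exclude this. The current version keeps all seven levels, the form states no restriction, and patients with reduced sorafenib would still not match.
- **The dose may be filled in at dispensing.** It sits beside patient-specific items, and the tick grid is not in the text available for review. However, the subject name, study ID and date dispensed carry no value while the dose does, and nothing marks it as an example. Level-specific diaries could exist outside the protocol, but none is mentioned.
- **Other safeguards exist.** The sorafenib drug information (7.4.4) requires patients to be instructed on taking the drug, and the diary gives a 24-hour contact for dose questions. This stands: the diary is not shown to be the controlling instruction, so the ratios are worst cases.

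Two stronger readings are tempting but not supported.

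- **That the diary corrupts the 75% evaluability rule in 14.1.1 and 14.2.** No section makes the diary a source for that rule. Section 9.0 lists pharmacy dispensing records among the source documents and does not name the diary, although its list is not exhaustive. The visible instruction is to tick a box per intake, which counts occasions rather than milligrams. Levels 1 to 6 are all twice daily, so induction days 10 to 19 give 10 × 2 = 20 occasions, and 75% is 15 of 20 whatever strength is shown. Only level -1 differs in frequency.
- **That patients will overdose at home in Cycle 1.** The request to bring unused tablets to hospital implies some use outside it, but no section says where the induction doses on days 10 to 19 are taken.

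**Conclusion.** The inconsistency stands. The sorafenib dose in Appendix E agrees with the protocol only for level 6 patients on unreduced sorafenib. Elsewhere it is higher than the assigned daily dose: 2 times at levels 1 to 4, 1.33 times at level 5, 4 times at level -1, and 1.33 or 2 times for a level 6 patient whose sorafenib is lowered by one or two levels.

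These figures rest on two assumptions: that Appendix E is issued as it appears, and, for actual exposure, that a patient follows it over other instruction. The documents give no basis for estimating how often that would happen. The point is an inconsistency between a patient form and the dosing sections. It touches no endpoint, sample size or error rate. It should still be corrected, because the form is patient-facing and the correction is simple.

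**What to change.** Reconcile Appendix E with 6.3, 6.10 and Appendix D. Either replace the stated dose and tablet count with fields completed at dispensing from the patient's current assigned dose, or supply one diary per sorafenib dose, labelled with the levels it serves. In both cases, issue a new diary whenever the sorafenib dose changes, including on entry to maintenance if the dose differs. Which dose applies to which patient is for the investigators to settle; no dose is proposed here. The cost is a form revision and its usual approval, with no change to the design or analysis.
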